Study Design and Procedures. Eighty (male=40, female=40) high treatment-interest daily smokers age 26-55 will be recruited from the local Pittsburgh community. As noted, past work has not revealed sex differences in CR, AAT, or tDCS training outcomes with smokers, but we will examine sex differences here. Participants will be screened via telephone interview, and again in person, for multiple measures including level of quit interest, assessed by asking subjects if they intend to quit smoking in the next 1, 3, 6, 12 months, longer, or never. Using a 2 x 2 design we will examine AAT (AAT, active control [AC]) X tDCS (active, sham) to reduce cue-induced craving and smoking topography, and attenuate behavioral and neurophysiological measures of attentional bias to combined personal smoking cues. We will also determine the impact of this novel CET methodology on daily smoking, intent and confidence to quit, and explore sex and other individual differences in the efficacy. Eligible participants will come to the laboratory and complete informed consent and further screening, including vision screening for sensory deficits that may affect cue reactivity and/or EEG testing, re-assessment of treatment interest and completion of forms. Participants will also undergo the semi-structured interview to identify the places of which to take pictures, and complete camera practice. After initial screening, participants will be randomized to one of the 4 groups (stratified by sex & age). Dropouts will be replaced but examined by AAT/tDCS group to assess tolerability. Groups include: 1) AAT + active (2.0 mA) tDCS, 2) AAT + sham (0.01 mA), 3) active control (AC) + active tDCS, or 4) AC + sham. Participants will participate in AAT/tDCS intervention sessions for 5 days over 3 weeks, but the over all study will be 10 visits total similar to our tDCS/schizophrenia study (DA0417742), and that by Mattai et al. Cue-induced craving, smoking topography, and attentional bias (reaction time & ERPs), as well as cigs/day intent to quit90 and confidence in quitting91 will be assessed at Week 1 Baseline sessions 1 & 2 and Re-test sessions 9 & 10 during Week 3. Cigs/day, intent and confidence to quit will be re-assessed during follow-up phone calls 1-week and 1-month post-training

3. Describe the primary and secondary study endpoints:

Primary:

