Visit 1: During this visit we will explain the study and all its procedures with the potential participant. If he/she agrees to participate and signs the consent we will move forward with visit 1 procedures. A carbon monoxide (CO) level will be measured by giving a breath sample using our breath CO monitor. If the participants CO level is below 8 ppm they will not be able to continue with the study and will be paid for today's visit and excused from the study.

The participant will complete the following forms:

- Smoking History: This form will ask questions about the participant and their smoking history and will also assess the participant's level of nicotine dependence.
- Quit Interest: This is a questionnaire for evaluating the participant's interest in quitting smoking.
- Intent to Quit: This measures the participant's degree of intention to quit smoking.
- Confidence in Quitting: This questionnaire assesses the participant's confidence in quitting smoking.

Next, we will identify personal smoking and non-smoking cues of places. The participant will go through a brief interview during which we will identify places in which they regularly smoke or do not smoke. We will lend them a camera and teach them how to take pictures before the next visit. The participant will take pictures of their top 4 places that are 'smoking cues' and 4 places 'non-smoking cues' from various angles. We ask that they don't take pictures of people (passers-by or any other friends/family in the pictures) or personal identifiers (license plates, street names, etc.) to protect privacy. The participant will bring the camera containing the pictures back with them to the second session during which time they will be checked to make sure they took the correct pictures identified and that they will work for the presentation program used in the study. If they do not the participant will be instructed to take more pictures to bring with them at the next scheduled visit.

Participants will be advised that they must not send any images that are considered distasteful, obscene, implicate legal action.

The participant will return the lent camera containing the pictures when they come back for the next study visit. We will also have the participant complete a brief vision test during this visit. They will stand 10 feet from an eye chart, identify and read out loud the line they can see most comfortably.

- The participant will be randomly assigned to one of four groups:

1. AAT + tDCS

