2. AAT + sham tDCS
3. AC + tDCS
4. AC + sham tDCS

The components of these groups are defined as:

- Approach/Avoidance Task (AAT): The participant will use a joystick to push and pull images in different directions on a computer screen.
- Transcranial Direct Current Stimulation (tDCS): is used to slightly change the way the brain works for a short time. One wet, thin sponge is placed on the participants head and another wet thin sponge is placed on their arm and connected to electrodes which will deliver a very weak electrical current. Before stimulation, their head and arm will be checked for any redness, irritation, or recent shaving of the head. If any of these are seen, we will exclude them from the study. Some participants may feel a slight painless tingling as the current begins, but the tingling should go away after a short time. tDCS will be given at 2.0 mA and stimulate the

dorsolateral PFC (dIFPC) the sham tDCS will be given at 0.01 mA. We will ask the participant at the beginning of and throughout the stimulation to report how much tingling they are feeling on a scale of 1 being "not at all" and 10 being "extreme". If at any point they are experiencing extreme discomfort, we will end the stimulation.

- Active Control (AC): The participant will assess the orientation of a picture and indicate it with a key press.
- Sham tDCS: Two wet, thin sponges are placed on the participants head and arm and the sponges will be connected to electrodes just as the actual tDCS but they will not deliver any electrical current.

Visits 2 and 9: During this visit the participant will have an attentional bias assessment while undergoing an electroencephalography (EEG).

- Attentional-Bias: You will be seated in front of a computer with a four-button color response box. Four different word lists of 15 words each will be presented in a random order with no repeats. For each trial, a cross appears in the center of the screen followed by one word from the list in one of four colors. You will press the button that matches the color in which the word appears.

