- EEG: The EEG allows us to measure electrical activity of the participants brain. A cap containing sensors will be placed on their head. In addition, sensors will be placed behind the ears, and on the tip of the nose. Gel will be inserted into the cap to connect the sensors to the scalp. The participant will not feel any sensations from these electrodes. While wearing the cap, they will complete the attentional bias training. Afterwards, we will clean as much of the gel from their scalp as possible.
- Cue-reactivity: Cue reactivity involves viewing pictures of the participants personal smoking-related and non-smoking-related pictures and rating how they felt while viewing those pictures. The pictures and the ratings are presented on a computer and some pictures will be projected on the wall.

Visits 3 and 10: During these visits the participant will complete cue-reactivity to their personal smoking and non-smoking cues and smoke cigarettes using a special cigarette holder that will measure how they smoke their cigarette. The participant will be given special instructions on how to light the cigarette and place it into the holder before they smoke. They will be seated comfortably in front of a large computer monitor and view 12 picture trials. Each picture trial will be followed by post-trial ratings. After all the picture trials, a screen will appear informing them that when pictures begin to appear again they may smoke (using the cigarette holder) as much or little as they like, or not smoke at all, it is up to them and watch the pictures. At any point while viewing these pictures they may start or stop smoking.

Visits 4-8: During these visits the participant will go through cue-reactivity while either doing AAT while receiving tDCS (Group 1), doing AAT while receiving sham tDCS (Group 2), doing AC while receiving tDCS (Group 3), or doing AC while receiving sham tDCS (Group 4). The participant will not specifically know which group they are in.

Follow-up: We will call the participants at 1-week and 1-month after visit 10 and ask them how many cigarettes per day they are smoking and ask them the intent and confidence to quit questionnaires.

2. Upload a copy of all materials used to collect data about subjects: (Attach all surveys, interview/focus group scripts, and data collection forms except for case report forms, SCID or KSADS):

Document	Category	Date Modified	Document History
View Environment Listing Sheet(2)	Data Collection	3/2/2023	History

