	Infrequent Risks	The risk associated with transcranial electrical stimulation is minimal. There is a small risk of skin irritation which is minimized by using saline water as the conductive medium, and through the monitoring of participant discomfort throughout the procedure. tDCS is seen as a non-invasive medical procedure, and the commonly reported side-effects in active vs. sham treatments are itching (39.3% vs 32.9%), tingling (22.2% vs 18.3%), headache (14.8% vs 16.2%), burning sensation (8.7% vs 10%), and discomfort (10.4% vs 13.4%). ¹⁰⁷ Redness at the electrode site has also been reported.
	Other Risks	No Value Entered

View	Research Activity	Cue-Reactivity
	Common Risks	Some of the stimuli used have been shown to significantly increase urge to smoke. The discomfort of increased urge to smoke is anticipated to dissipate fairly quickly, and over the course of the treatment may lead to less robust responses.
	Infrequent Risks	No Value Entered
	Other Risks	No Value Entered

View	Research Activity	Collection and storage of private information
	Common Risks	No Value Entered
	Infrequent Risks	There is a rare possibility of a breach of confidentiality, but we have safeguards in place to minimize that. All records related to your involvement in this research study will be stored in a locked file cabinet and all electronic records are password and firewall protected. Your identity on these records will be indicated by a case number rather than by your name, although we may use your initials on certain forms.
	Other Risks	No Value Entered

2. * Describe the steps that will be taken to prevent or to minimize risks:

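### Skin signs seen before stimulation lead to exclusion after randomisation, and the plan does not say that those excluded are followed up and analysed in their assigned group

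*Combined protocol and SAP*

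**What the plan says.** **Order of events.** Study Design, item 2, places randomisation after initial screening. Research Activities, item 1, lists it under Visit 1: "The participant will be randomly assigned to one of four groups". Stimulation, active or sham, is given only at Visits 4-8. Study Design, item 2, describes the course as follows: "Participants will participate in AAT/tDCS intervention sessions for 5 days over 3 weeks".

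**The check.** The tDCS bullet in Research Activities, item 1, says: "Before stimulation, their head and arm will be checked for any redness, irritation, or recent shaving of the head". The next sentence gives the consequence: "If any of these are seen, we will exclude them from the study". For extreme discomfort, the same bullet says only that stimulation will be ended. The sham bullet does not mention the check.

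**Skin effects.** Risk and Benefits, item 1 (tDCS), lists a small risk of skin irritation and adds: "Redness at the electrode site has also been reported".

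**Entry criteria.** Study Design, item 6, lists scalp irritation as an exclusion. It does not list recent head shaving or skin signs on the arm.

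**What follows a loss.** Study Design, item 2: "Dropouts will be replaced but examined by AAT/tDCS group to assess tolerability". Item 8 repeats this and fixes 20 per group. No analysis population is defined. Risk and Benefits, item 8, keeps data gathered before a participant leaves but describes no outcome collection afterwards.

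**The concern.** An exclusion made after randomisation is harmless only if it is unrelated to the assigned arm or unrelated to outcome. Here two of the three triggers, redness and irritation, are also listed as effects of the procedure. If people leave because of what stimulation did to their skin and are replaced, the active arms come to consist of people who tolerate stimulation, while the sham arms may be selected differently or hardly at all. The tDCS main effect would then no longer compare the groups formed by randomisation. A comparison of dropout by group would reveal an imbalance but would not remove its effect on the estimate.

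**Working it through.** The plan states no rate of redness or of exclusion, so there is no figure of its own to reproduce on this point. The check is therefore the order of events, followed by an illustration with assumed rates.

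**1. Does exclusion follow randomisation?** Yes, on the text. Assignment is at Visit 1, the first stimulation is at Visit 4, and the check is tied to stimulation.

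**2. Can it depend on the arm?** This turns on a detail the text leaves open.

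- *Check repeated before each of the five sessions.* The checks at Visits 5-8, up to four of them, follow an earlier stimulation. Redness or irritation from that stimulation could trigger exclusion. Active arms receive 2.0 mA. Sham is given as 0.01 mA in two places and as no current in the sham bullet.
- *Check made once, before Visit 4.* Exclusion still follows randomisation, but no earlier current can have caused the sign.

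**3. How many might be lost? (assumed rates)** With probability p of a finding at each of four later checks, the cumulative loss is 1 − (1 − p)^4. There are 40 participants at each level of tDCS (2 groups × 20).

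| p per check | Cumulative loss | Of 40 |
|---|---|---|
| 1% | 3.9% | 1.6 |
| 2% | 7.8% | 3.1 |
| 5% | 18.5% | 7.4 |
| 10% | 34.4% | 13.8 |

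**4. How far would the contrast move? (assumed rates)** Let e₁ and e₀ be the fractions excluded in active and sham, and g the outcome difference in SD between excluded and retained participants, the same in both arms. The mean of those retained moves by e × g in each arm, so the contrast shifts by b = (e₁ − e₀) × g.

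The standard error uses the plan's own R² of .3: residual SD √0.7 = 0.837, and SE = 0.837 × √(2/40) = 0.187. As a check on this SE, the plan's daily-smoking effect of 0.58 gives 0.58/0.187 = 3.10 and two-sided power of 0.873 (0.864 with the t distribution). That agrees with the plan's figure of above 0.84.

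Type I error is 1 − Φ(1.96 − b/SE) + Φ(−1.96 − b/SE).

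| Excluded, active v sham | g | Shift b (SD) | Type I error |
|---|---|---|---|
| 10% v 2% | 0.25 | 0.08 × 0.25 = 0.02 | 0.051 |
| 10% v 2% | 0.8 | 0.08 × 0.8 = 0.064 | 0.064 |
| 20% v 5% | 0.25 | 0.15 × 0.25 = 0.0375 | 0.055 |
| 20% v 5% | 0.8 | 0.15 × 0.8 = 0.12 | 0.098 |
| equal rates | any, same in both arms | 0 | 0.050 |

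The shift is also zero if g = 0.

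**5. Do the two lists agree?** No. Someone who meets every criterion in Study Design, items 5 and 6, can still be excluded under Research Activities, item 1, for recent head shaving or an arm skin sign, after assignment. This holds on either reading of step 2.

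**The case against.** The strongest reply is that this is an eligibility rule placed under the wrong heading. Scalp irritation is already an entry exclusion, the sentence uses the language of eligibility, and it sits in a general description of the group components, tied to no visit. On that reading the check may be made once and redness from current is irrelevant. This is a fair reading, and the text does not rule it out. It does not change the fact that the check comes after assignment as scheduled.

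A reader might go further than the documents allow in four ways.

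- *That the check is made at every session.* This is natural for a procedure given five times, but it is not stated.
- *That excluded participants are certainly replaced.* Replacement is stated for dropouts. Removal by the researchers is described separately (Risk and Benefits, item 7), with no mention of replacement. The fixed group size makes replacement probable.
- *That active participants will be lost more often, with none lost in sham.* Sham uses the same wet sponges at the same sites. Redness is not split by arm, and nothing shows that it lasts to a later visit. The comparative rates given for active v sham differ little and are sometimes higher in sham: itching 39.3% v 32.9%, tingling 22.2% v 18.3%, headache 14.8% v 16.2%, burning 8.7% v 10%, discomfort 10.4% v 13.4%.
- *That shaving cannot be screened before assignment.* It is only absent from the listed criteria. The phone screen is an attachment not reproduced here, and nothing links shaving to the arm.

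The plan also has safeguards: dropout by group, adverse-event monitoring at each laboratory visit, and quarterly review of attrition. These would make intolerance visible. They do not supply outcomes after exclusion or restore the comparison.

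**Conclusion.** The point holds in a limited form. As scheduled, the rule excludes people from the study after randomisation, they are probably replaced, and the plan neither follows them nor commits to analysing them as assigned. Whether exclusion can depend on active v sham rests on the check being repeated, which is not stated, and on skin signs differing by arm, for which no rate is given. Bias is therefore possible rather than shown.

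Under the assumed rates above, the shift in the tDCS contrast runs from nil to about 0.12 SD, with type I error from 0.05 to about 0.10. The upper end needs both a large imbalance (20% v 5%) and excluded participants who differ strongly (0.8 SD). The documents do not support saying that the randomised comparison is broken, particularly in a trial that describes itself as exploratory. The change is still worth making, because it removes an avoidable risk at the cost of a few sentences.

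**What to change.** 1. Reconcile the exclusion list (Study Design, item 6) with the skin check (Research Activities, item 1). State whether the check is an eligibility criterion or a reason to withhold stimulation, when it is made and whether it is repeated, and that it is identical in all four arms. Reconcile the two descriptions of sham current at the same time.
2. Leave any decision about stimulation to the investigators, but separate it from retention in the trial. A participant with skin signs after randomisation stays in the trial, and Visits 9-10 and both follow-up calls are collected where the participant agrees.
3. Define the primary analysis population as all randomised participants in their assigned group. Extra recruitment is compatible with this, provided a new participant does not displace one already randomised.
4. Report exclusions for skin signs by arm, separately from other dropouts.

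**Cost.** Protocol and analysis wording, plus outcome visits for a few more people. Some participants will be analysed with incomplete training, which dilutes the estimate slightly. As an upper bound, if a fraction e of the active participants gained nothing, an effect of 0.58 would become 0.58 × (1 − e): 0.52 at an assumed 10% and 0.46 at 20%. Partial training would make the loss smaller.

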AAT/tDCS sessions of personal combined-cue exposure, with follow-up assessments of cig/day, intent and confidence to quit at 1 week and 1-month post-training.

Our specific goals are:

Aim 1: Determine the effectiveness of AAT and tDCS to attenuate cue-induced

craving and attentional bias to personal smoking stimuli. AAT, tDCS, and combined AAT + tDCS will each lead to greater reductions in pre-post training cue-induced craving and improved behavioral (quicker reaction time) and neurophysiological (lower P300 ERP) measures of attentional bias for smoking cues over the control condition.

Aim 2: Determine the effectiveness of AAT and tDCS to reduce cue-provoked smoking behavior and daily smoking, and to increase intent and confidence to quit. AAT, tDCS, and combined AAT + tDCS will

each lead to greater pre-post-training reductions in smoking topography measures (latency to light & puff volume) assessed during cue exposure, as well as reduced cigs/day and increased confidence and intent to quit from pre-training to post-training and 1-week & 1-month follow-up over the control condition.

Aim 3: Examine if changes in reactivity to smoking-related cues (Aim 1) are associated with posttraining reductions in smoking topography and/or cig/day and increases in intent and confidence to quit. (Aim 2). Reduced craving and attentional bias to smoking stimuli across all groups will be associated with reductions in smoking topography post-training, as well as post-training and follow-up changes in cigs/day and confidence and intent to quit Secondary Aim: Explore sex and other individual differences as moderators of outcome measures to explore who might benefit most from AAT and tDCS methods.

There have been few recent innovative approaches for alleviating cue-induced craving to smoke. AAT and tDCS are two promising methods to newly apply to this endeavor. Although this exploratory work is not fully powered to detect significant interaction effects of AAT and tDCS, we will examine the size of the interaction to inform potential efficacy trials of combined AAT + tDCS vs the individual therapies alone. The results here will thus guide a future RCT of novel CET methodology within a cessation trial aimed at helping more smokers stay quit.

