starkly different than those proposed here. Further, CR varies by drug/substance of choice, with reactivity to alcohol and food cues being notably less robust and less affected by the same manipulations as smoking. One alcohol study, found no effect of 1 weekly tDCS session for 4 weeks on attentional bias and craving in college drinkers, and three others, also using limited tDCS, showed no changes in attentional bias, but revealed craving reductions. One food study found null results after 1 tDCS + cognitive modification session to reduce chocolate craving. Smoking tDCS studies suggest that multiple sessions closely spaced increase efficacy, thus we propose 5 closely spaced sessions of tDCS during personal smoking cue exposure. No studies have used personal cues from participants lives, pre-post cue reactivity assessment of craving and behavior, or highly dependent individuals. No studies, including smoking, have examined combined tDCS + AAT. Thus, although the proposed work is high risk, past null findings across other substances using generic cues and focusing on attentional bias do not predict null effects here, rather extensive past work on each of our included components and strong theory behind combining tDCS + AAT suggest potential for high reward. Assessing the impact of novel CET on smoking-related outcome measures. Attentional Bias. Smokers demonstrate selective attention to smoking-related stimuli. and delayed reaction time (RT) during exposure to smoking cues. They are slower than controls to color-name smoking-related words in a modified Stroop task, which combines common words with intermittent presentation of smoking-related words. Smokers maintain their gaze on smoking stimuli longer than neutral stimuli, and show increased P300 response to smoking-related cues. The smoking-cue P300 is thought to reflect attentional and motivational state of smokers when cues prime smokers' urge to smoke. According to incentive-sensitization theory, these biases likely emerge from the motivational and attention-grabbing properties of smoking cues, which gain salience after repeated pairing with smoking. This causes sensitization of dopamine neurotransmission in the striatum increasing the salience of the stimuli long-term and resulting in greater allocation of attentional resources (attentional bias) and increases in craving. Abstinent smokers with greater attentional bias to smoking stimuli are more likely to relapse, reducing this response may aid cessation. In our pilot studies, we assessed attentional bias behaviorally and using EEG, in a forced-choice RT task and found a decreased RT difference between smoking and neutral stimuli of 60% ($p<0.05$) following tDCS. We also show that tDCS of right dlPFC using the same montage proposed here (N=8) reduced the P300 difference between smoking and nonsmoking images compared to sham tDCS (N=8) in smokers with long-term/chronic schizophrenia (Figure 2). In the proposed study, we anticipate that AAT and tDCS training will reduce approach bias indexed as decreased RT and P300 amplitude difference between smoking and neutral images from baseline to re-test during a modified smoking Stroop task. Cue-Induced Craving and Smoking. As noted above, smokers report that smoking cues are a major obstacle to quitting and multiple studies have demonstrated robust cue-induced craving, cue-induced smoking behavior, and a strong link between the two. Our procedures to personalize cues, present them in combination, and assess smokers' self-report and behavioral CR creates an ideal environment to develop and test novel CET methodology. Although the combination of AAT + tDCS has not been assessed for reduction of cue-induced reactivity (craving or smoking topography), research on these two procedures independently have examined AAT effects on attentional bias and daily smoking, and tDCS effects on cue-provoked craving and daily smoking, with mixed but largely positive effects. Given that tDCS is known to be more effective when it is used while engaging the neural processes targeted for change, we anticipate that combining AAT + tDCS during cue exposure may further enhance reduction in cue-induced craving and smoking topography (latency & puff volume) to combined personal smoking cues (proximal, environment, and people) as measured at baseline and re-testing after 5 sessions of training. Daily smoking (cigs/day) and Intent and Confidence to quit. Both AAT and tDCS have independently shown efficacy in reducing daily smoking among non-quitting smokers with high treatment

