in this experimental study will be replaced. We will examine differential group dropout to assess tolerability of methods. Limited past work leads us to constrain our power analysis to AAT and/or tDCS for each variable, but we expect the synergistic effects of combined AAT + tDCS to be even greater, making these power analyses conservative. However, this exploratory work is not fully powered to detect significant interaction effects. Aim 1. Craving and Attentional bias. Assuming a Cohen's d effect size (ES) of 1.02- 1.57 based on prior literature, a multivariate $\alpha = .05$, and an R2 of .3 from other covariates in the model, we expect to have greater than 0.99 power to detect main effects of tDCS on cue-induced craving. Boggio et al.⁴¹ found an ES of $d=1.13$ for reduction in cue-induced craving via tDCS. Our pilot P300 EEG data from our current study in smokers with schizophrenia shows ES of $d=1.3$. AAT work indicates post-training

attentional approach bias reductions to smoking cues of $d=1.2629$, thus we expect greater than .80 power to detect changes in attentional bias. Aim 2. Smoking topography and cig/day. Based on our past cue studies, smoking topography to multiple cues are of similar magnitude to cue-induced craving ($d=.90$). Further, past tDCS studies of daily smoking outcome show an ES of 0.58100. Thus, with a multivariate of $\alpha=.05$, 20 subjects per group, and an R2 of .3, we expect greater than 0.84 power to detect an effect of tDCS on smoking behavior in both the MANCOVA assessing immediate effects on smoking behavior and the RM-MANCOVA assessing longitudinal effects on cig/day and intent & confidence to quit. Again, tDCS

+ AAT should enhance effects. Aim 3. Smoking prediction. Assuming $\alpha=0.17$ (conservative adjustment for 3 outcome variables) and controlling for other variables contributing an R2 of .3, we will have power greater than .99 to detect an R2 of 0.2422 or larger, in the model predicting smoking topography and cig/day from cue-induced craving and attentional bias change scores.

Research Activities

1. * Provide a detailed description of all research activities (including screening and follow-up procedures) that will be performed for the purpose of this research study. This description of activities should be complete and of sufficient detail to permit an assessment of associated risks.

The PI, Co-I's and Research Coordinators will be responsible for carrying out all the research activities.

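### Aim 1 claims attentional bias to personal smoking cues, but the only reaction-time and EEG task described uses word lists, so the results can support a conclusion about smoking-related words only

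*Combined protocol and SAP*

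**What the plan says.** **The target.** Study Aims, item 1 opens Aim 1 with "craving and attentional bias to personal smoking stimuli". The hypothesis paragraph before it names Stroop and EEG among the indices of reactivity to personal combined cues. Study Design, item 2 repeats the target as "neurophysiological measures of attentional bias to combined personal smoking cues". Study Design, item 3 lists RT and ERPs under a primary endpoint headed as cue reactivity to personal cues.

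**The definition.** The attentional-bias text in Study Aims, item 2 anticipates "decreased RT and P300 amplitude difference between smoking and neutral images from baseline to re-test during a modified smoking Stroop task".

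**The procedure.** Research Activities, Visits 2 and 9, describes one attentional-bias task: "Four different word lists of 15 words each will be presented in a random order with no repeats". Each trial shows a cross, "followed by one word from the list in one of four colors", and the participant presses the button for that colour. EEG is described for this task alone: "While wearing the cap, they will complete the attentional bias training". Personal pictures appear at the same visits in the cue-reactivity block, where the participant views and rates them. No RT or ERP outcome is named for that block.

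**The planning value.** Study Design, item 8 states: "Our pilot P300 EEG data from our current study in smokers with schizophrenia shows ES of" 1.3. Study Aims, item 2 describes a P300 pilot comparing smoking with nonsmoking images, 8 active v 8 sham, in smokers with schizophrenia.

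**The concern.** Personal cues are the study's stated remedy for past failures of cue-exposure treatment, so whether bias is measured on personal stimuli is central to Aim 1. If the claim stays personal and the measurement stays verbal, a null result could be misread as no change in bias to the personal cues used in training, and a positive result as proof of such a change. The word task supports neither reading.

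Both attentional-bias measures are affected. Aim 3 then uses attentional-bias change scores as predictors of smoking outcomes, and the results are meant to guide a later trial.

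The planning value raises a smaller, separate question: it comes from images, and the plan gives no effect size for a word task.

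**Working it through.** **1. The sections side by side**

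| Place | Stimulus for attentional bias |
|---|---|
| Study Aims, item 1 (hypothesis and opening of Aim 1) | personal |
| Study Design, item 2 | personal, combined |
| Study Aims, item 2 (definition) | smoking v neutral images, in a modified Stroop |
| Study Design, item 3 | smoking stimuli, under a personal-cues heading |
| Study Design, item 8 | smoking-related cues |
| Research Activities, Visits 2 and 9 (procedure) | four lists of 15 words, content not given |

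The image-based definition has no matching procedure, and neither does the personal target. The task described yields RT and P300 on words.

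**2. Reproducing the stated power**

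Inputs from Study Design, item 8: 20 per group in four groups, so a main effect compares 40 v 40; alpha .05 (taken as two-sided); R2 of .3 from covariates; d=1.3 for P300 and d=1.26 for AAT approach bias (the digits 29 after 1.26 are read as a citation number). The stated power is greater than .80.

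Noncentrality = d × sqrt(40/2) / sqrt(1 − R2).

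- d=1.26: 1.26 × 4.472 = 5.63 with R2=0, and 5.63/0.837 = 6.73 with R2=.3.
- d=1.3: 1.3 × 4.472 = 5.81 with R2=0, and 5.81/0.837 = 6.95 with R2=.3.

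Power is 0.9998 or more in every case. Even a 20 v 20 contrast gives 0.97 to 0.998. The stated bound reproduces.

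**3. How small the word-task effect may be**

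The plan offers no word-based effect size, so only a threshold can be given. Power of 0.80 with about 75 residual df needs a noncentrality of about 2.84.

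- R2=.3: d = 2.84/4.472 × 0.837 = 0.53, which is 41% of 1.3.
- R2=0: d = 2.84/4.472 = 0.63 (0.635 before rounding), which is 49% of 1.3.

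| Word effect as share of 1.3 | d | Power, R2=0 | Power, R2=.3 |
|---|---|---|---|
| 75% | 0.975 | 0.99 | 1.00 |
| 50% | 0.65 | 0.82 | 0.93 |
| 40% | 0.52 | 0.63 | 0.78 |
| 25% | 0.325 | 0.30 | 0.40 |

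The plan specifies a multivariate test. Take three outcomes, an effect on one only, and outcomes treated as uncorrelated: the noncentrality is (80/4) × d²/(1 − R2), on 3 and 71 df. The threshold rises to d=0.64 (R2=.3) or d=0.76 (R2=0).

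**The case against.** The strongest reply is that the plan never binds the measure wholly to personal images. Its background presents colour-naming of smoking-related words in a modified Stroop as a recognised index of attentional bias, which is the task described. The predictive sentence of Aim 1 speaks of smoking cues, the endpoint line of smoking stimuli, and the analysis section of smoking-related cues, all without the word personal. The Innovation text attaches personal to craving and not to the Stroop and EEG measures. On power, the above-.80 statement directly follows the AAT value of 1.26, whose stimulus type is not stated, so it does not rest on the image pilot alone.

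All of this stands, and it rules out three stronger readings:

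- **That attentional bias is not measured at all.** RT and P300 are collected on words. Only the personal or image-based version lacks a procedure.
- **That the pilot effect fails to carry over, or that the study is underpowered for this outcome.** Nothing in the documents shows a smaller effect on words. They simply give no basis for carrying 1.3 across, and the population differs as well.
- **That the task certainly tests transfer to untrained, generic words.** The content of the four lists is never given.

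The reply does not remove the conflict. The opening of Aim 1, the hypothesis, Study Design item 2 and the endpoint heading all still say personal, the definition still says images, and the procedure still says words.

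**Conclusion.** The conflict is real and limits what Aim 1 can conclude. Followed as written, the plan supports a statement about bias to smoking-related words, on the assumption that some of the four lists are smoking-related. It does not support a statement about bias to personal smoking cues or to images.

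The power figure is unsupported for this task rather than wrong. For a univariate 40 v 40 main effect at two-sided .05, it tolerates a fall to between 41% and 49% of the pilot value before dropping below 0.80. The margin is narrower for the three-outcome multivariate test.

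**What to change.** 1. Reconcile the hypothesis and Aim 1 (Study Aims, item 1), the definition (Study Aims, item 2), Study Design items 2 and 3, and the task description for Visits 2 and 9. State whether the RT and P300 outcomes use words or images, and personal or generic stimuli.
2. If the word task stands, restate the outcome and its conclusion as the RT and P300 difference between smoking-related and neutral words. Give the content of the four lists and the bias score, and do not report the result as bias to personal cues.
3. In Study Design, item 8, label d=1.3 as an image-based pilot assumption from smokers with schizophrenia. Add that power above .80 for a 40 v 40 main effect holds on the word task only if d is at least about 0.53 (R2=.3) or 0.63 (R2=0).

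The cost is wording, with no change to sample size or visits if the word task stands.

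Recording EEG during the personal-picture block is at most an optional exploratory addition. Pictures are first checked at Visit 2 and may have to be retaken, so some baselines could be missing. No trial count or event timing is given for the block at those visits. The gel appears to be cleaned off before it. It would also supply no RT measure.
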